9.2.2 Exclusion Criteria

All females in the age group 13 to 49 years with available information that they are not of childbearing potential before initiation of oral retinoids (such as records of hysterectomy or sterilisation) will be excluded.

Data for the oral retinoids acitretin, alitretinoin, and isotretinoin will only be extracted from databases in target countries where the respective active substance has been granted market authorisation.

No further exclusion criteria will be applied.

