9.7.1 General Considerations

Given the study objectives the analyses will be mainly descriptive and will be conducted by country, by active substance and study time periods (both pre-implementation periods and post-implementation period). To allow for analysis across all data sources used in the study, a meta-analytic approach will be used to assess and pool the results from the four study countries together for each active substance (see 9.7.3.4).

The analyses will be provided for the overall class of oral retinoids and for the single active substances. Categorical variables will be presented as counts (n), proportions (%) with CI where relevant as for parameters used to address the primary objective and for the comparison of the incidence of exposed pregnancies. Continuous variables will be presented as means with standard deviation (SD) and as medians with interquartile range (IQR), where appropriate.

Changes in the reimbursement policy for contraceptives in the healthcare systems of the study countries will be considered to discard any differential misclassification of exposure.

The statistical unit will be the oral retinoid treatment episode and patient as well as prescription where appropriate. Patients who have multiple treatment episodes of oral retinoid use will be entered the cohort for analysis more than once.

The term “use” in the context of the analysis refers to the prescription or dispensing of drugs or IUD.

In the analysis, prescriptions of patients will be followed from the exposure start date to censoring date, i.e., transfer out of the database incl. death or the end of the study period, whichever comes first.

Statistical analyses will follow the tables shells validated by the MAH consortium and will be displayed using tables, listings and/or graphs. The statistical analysis will be conducted using SAS or an equivalent statistical analysis software. A detailed statistical analysis plan (SAP) will be prepared prior to data extraction.

The statistical results of all target countries and all active substances will be presented in a single report.

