9.7.2 Main analyses

The main analysis will cover the prescribing and monitoring patterns of oral retinoids during the pre- and post- implementation periods in females of childbearing age (13-49 years of age, inclusive) to meet the primary study objective. The analysis will be descriptive in nature. The first oral retinoid prescription of a treatment episode will be considered as exposure start date for the analyses of treatment episodes.

Measures related to the PPP

The following analyses will be performed:

- Laboratory pregnancy tests
 - Percentage of patients with laboratory pregnancy test performed at treatment start (up to 7 days before exposure start date)
 - Percentage of patients with laboratory pregnancy tests performed during treatment
 - Percentage of patients with laboratory pregnancy tests performed monthly according to the SmPC during treatment
 - Frequency of laboratory pregnancy tests during treatment, by month of treatment
 - Percentage of patients with laboratory pregnancy tests performed after treatment stop
 - For all retinoids: percentage of patients with laboratory pregnancy test performed within two months after treatment stop
 - For acitretin: performance of laboratory pregnancy tests beyond 1 month up to 3 years after treatment stop (depending on the length of individual follow-up of patients)
- Contraceptives

- Percentage of patients with prescription of hormonal contraceptives before treatment start (up to 3 months before the exposure start date or longer depending on the type of contraceptive)
- Percentage of patients with use of IUDs before treatment start (up to 5 years before exposure start date)
- Percentage of patients with concomitant use of contraceptives (hormonal contraceptives and / or IUD) during treatment
- Percentage of patients with use of contraceptives (hormonal contraceptives and / or IUD) within two months after treatment stop
- For acitretin: percentage of patients with use of contraceptives (hormonal contraceptives and / or IUD) beyond 1 month up to 3 years after treatment stop (depending on the length of individual follow-up of patients)
- Periodicity of oral retinoid prescriptions
 - Time interval between prescription dates for oral retinoid prescriptions during treatment (in days)
 - Proportion of oral retinoid users with monthly prescription intervals during treatment

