It is aimed to include all patients with oral retinoid prescriptions in the analyses. However, a history of at least 3 months is necessary to cover prescriptions and laboratory pregnancy tests before treatment initiation. Analyses after treatment initiation will be performed for the following scenarios: (a) patients with a follow-up available covering the treatment episode and (b) patients with a follow-up beyond the treatment episode of at least 2 months.

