9.7.3 Secondary analyses

9.7.3.1 Patient age, indication and prescriber specialty

The following analyses will be performed:

- Patient age (mean age, by age groups, 13-20 years, 21-35 years, 36-49 years)
- Indication (diagnosis related to the oral retinoid prescription at the day of oral retinoid prescription or in the last 12 months before oral retinoid initiation)
- Prescriber specialty (Germany, Spain, and Sweden; not available for France)

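### The three-month history rule does not match the five-year IUD look-back, so short-registered women can be counted as having no IUD

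*Protocol*

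**What the plan says.** Section 9.7.2 states the aim and the history rule together: "It is aimed to include all patients with oral retinoid prescriptions in the analyses", but "a history of at least 3 months is necessary to cover prescriptions and laboratory pregnancy tests before treatment initiation". This is the only pre-treatment history requirement in the protocol. On eligibility, section 9.2.2 adds that "No further exclusion criteria will be applied".

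The measures that rely on that history have different look-backs:

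- IUD, part of the primary objective (9.7.2): "Percentage of patients with use of IUDs before treatment start (up to 5 years before exposure start date").
- Hormonal contraceptives, part of the primary objective (9.7.2): "up to 3 months before the exposure start date or longer depending on the type of contraceptive".
- Indication, a secondary measure (9.7.3.1): "diagnosis related to the oral retinoid prescription at the day of oral retinoid prescription or in the last 12 months before oral retinoid initiation".

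Section 9.7.1 says that use in the analysis "refers to the prescription or dispensing of drugs or IUD". Section 9.7.2 also has combined measures during and after treatment, in which a hormonal method or an IUD counts. These too depend on seeing an insertion that may lie years back.

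**The concern.** Three months fits short-acting hormonal methods and the 7-day pregnancy-test window. It does not fit a device that stays in place for years. Take a woman who joined her insurer or practice 4 months before her first retinoid prescription and had an IUD fitted 2 years earlier. She meets the history rule and has no visible insertion record. Because use is defined by a record, she enters the IUD percentage as having none. Her status is in fact unknown.

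Contraception before, during and after treatment is a primary-objective element, compared between periods and pooled across four countries. Counting unobservable women as having no IUD lowers the measured level and shrinks a true change. If length of registration differs between periods or countries, part of that difference can pass for a difference in contraceptive practice.

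**Working it through.** **The rules side by side**

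| Measure | Look-back | Required history | Share of window visible at the minimum |
|---|---|---|---|
| Short-acting hormonal | 3 months | 3 months | 3/3 = 100% |
| Long-acting hormonal | longer, by type | 3 months | below 100%, not stated |
| IUD | 60 months | 3 months | 3/60 = 5% |
| Indication | 12 months | 3 months | 3/12 = 25% |

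The protocol has no figure of its own on this point. The visible share is min(1, history / window) and assumes records spread evenly over the window. For the IUD window it is 10% at 6 months of history, 20% at 12, 40% at 24 and 60% at 36.

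**Does anything else in the protocol correct this?**

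- Section 9.7.6 adjusts denominators for missing values. An unseen insertion leaves no missing value, only the absence of a record.
- Section 9.7.4 has two sensitivity analyses. One widens the test window to a month and the other drops the first 6 months after distribution of the materials. Neither varies history.
- After treatment, section 9.7.2 does match observation to window: it uses women with at least 2 months of follow-up alongside the two-month measures, and it makes the 3-year acitretin measures depend on individual follow-up. Before treatment it does no such matching for IUDs.

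**Does the start of the databases cause the gap?** The first study period opens in July 2014. Usable data begin in 2009 in France, 2004 in Germany, 2005 in Spain and July 2005 in Sweden. With January starts assumed except for Sweden, that leaves 5.5, 10.5, 9.5 and 9.0 years. All exceed 5 years, so the gap can come only from a woman's own registration.

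**Illustrative size.** The protocol gives neither IUD prevalence nor the distribution of history, so both are assumptions. Let π be true prevalence and s the share of women with only 3 months of history, the rest having 5 years and no later code helping. Then observed prevalence = π × [1 − s × (1 − 3/60)] = π × (1 − 0.95s).

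| π | s = 10% | s = 30% | s = 50% |
|---|---|---|---|
| 5% | 4.5% | 3.6% | 2.6% |
| 10% | 9.1% | 7.2% | 5.3% |
| 20% | 18.1% | 14.3% | 10.5% |

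If s differs between periods by Δ, the false difference is π × Δ × 0.95. For Δ = 10 points it is 0.5, 1.0 and 1.9 points at π = 5%, 10% and 20%. For Δ = 20 points it is 1.0, 1.9 and 3.8 points.

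A milder case: 30% of women have 24 months and the rest 5 years. Sensitivity is 0.7 × 1 + 0.3 × 0.40 = 0.82, and a true change of 5 points shows as 5 × 0.82 = 4.1.

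**The case against.** The case against is substantial.

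- *The 3-month sentence is a floor and names only prescriptions and pregnancy tests.* True, and the protocol nowhere says that short-history women are scored as having no IUD. But section 9.3.2 lists IUDs as prescriptions, section 9.7.1 ties use to a record, and no longer requirement is set. Reading the 5 years as a maximum over whatever is available leaves each woman measured over a different window.
- *Denominators belong in the SAP.* A missing denominator rule would not be a finding. Here a history rule is stated, and it does not fit the look-back stated in the same section.
- *Insertion is not the only trace.* Annex 3.2 lists Z97.5, Z30.5 and T83.3, each of which can reveal an older device within a short history. This stands, and it makes the 5% a worst case. How many women it rescues is unknown.
- *Coverage is broad.* Sweden is national, France covers about 88% of the population and SIDIAP over 80% of Catalonia's, so short registration may be uncommon. In Germany, where a change of insurer is the likeliest cause, only 2% of women above 20 had a contraceptive record, so reimbursement probably dominates under-capture. Both points limit the size.
- *Under-recording is already disclosed.* Section 9.9.2 expects it in both periods, but attributes it to undocumented and non-reimbursed methods. Presence in both periods does not show that available history is equal.

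A reader might infer that the pre/post comparison is biased in a known direction. The documents do not support that: nothing shows that history differs between periods, and the database start dates create no asymmetry. A reader might also put indication on the same footing. It is secondary, the error is a diagnosis not found, and a same-day diagnosis is visible whatever the history.

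**Conclusion.** The mismatch is real and sits in the stated rules. As written, women registered for less than the look-back can be counted as having no IUD, unless a later code shows the device. The same holds for long-acting hormonal methods and for the combined measures.

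The effect on level is downward. The effect on the comparison between periods or countries is unknown in size and direction. The 5% visible share assumes evenly spread insertions and no later code, and the prevalence tables rest on assumed shares with no source in the protocol. The bias may well be small where registration is near-complete. This is an inexpensive improvement to a primary-objective measure, not a defect that undermines the study. Requiring 5 years of history as the sole primary denominator would be a trade-off against the aim of including all patients, and the protocol does not compel it.

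**What to change.** In sections 9.7.2 and 9.7.4:

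- Keep the all-patient analysis with the 3-month rule.
- Add the IUD measure and the combined hormonal and/or IUD measures in women with at least 5 years of history. For long-acting hormonal methods, require history equal to the look-back for that type.
- Apply the restriction identically in all periods and countries.
- Report the distribution of available history by period and country, so that a reader can see whether it differs.
- For indication, report the share of women with less than 12 months of history.

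The data reach back far enough, and section 9.4.1.2 lists time insured among the German variables. The cost is one denominator rule per measure and less precision in the added analysis. Table 4's formula gives 1.96² × 0.5 × 0.5 / 0.05² = 384.2, hence the protocol's 385 women for ±5 points at 50%. On the German feasibility count in Table 5, 3,729 women give ±1.6 points at 50%; if half had 5 years of history (assumed), 1,864 would give ±2.3. For the 153 German acitretin users, the same halving to 76 moves ±7.9 to ±11.2, so by-substance results in small groups would be indicative only.

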9. RESEARCH METHODS

9.1 Study Design

This is a multicounty, multisource, observational cohort study in females of childbearing potential receiving oral retinoids (i.e., acitretin, alitretinoin and isotretinoin) using established data sources in different European countries (i.e., France, Germany, Spain, and Sweden)

The study will employ a pre-post design to evaluate the effectiveness of the implementation of the updated RMMs with respect to the PPP according to the following schedule:

- Pre-implementation period: period prior to the date of the implementation of the updated RMMs
- Post-implementation period: period after the implementation of the updated RMMs

Periods will be defined as (also see Figure 1):

Pre-implementation period: The period before the implementation of the updated RMMs. The RMM tools will be distributed in the fourth quarter 2018 (the exact date may vary depending on the country). The pre-implementation period captures two periods:

- Pre-referral: the 2-year period before referral start in July 2016. This period will be used for the before and after comparison with the post-implementation period.
- Post-referral: the 2.5-year period between the referral start date in July 2016 and the distribution of the RMM tools in the target countries (assumed until December 2018). The duration of this period may vary depending on the duration of the approval and the distribution of the RMM tools in each country.

Post-implementation period: This period captures the time starting after the distribution of EM until December 2020. The start date of the period in each country will depend on the date on which the EM is approved by the respective national competent authorities.

The final dates of the study periods depend on the final schedule of the implementation of the updated RMMs in each country.

Figure 1: Overview of study periods

A single database for all target countries is not available. Therefore, a study approach was chosen which includes multiple data sources to gather drug utilisation data for oral retinoids (acitretin, alitretinoin and isotretinoin) in the European countries of interest.

Databases with longitudinal secondary patient data collected continuously over time will be used preferably to provide the most comprehensive data for the outcomes of interest.

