9.7.3.4 Meta-analysis

To account for any differences between the databases with regard to their format and to allow for differences in the population of patients treated with isotretinoin, acitretin, and alitretinoin, and differences in adherence to PPP measures in those populations, a meta-analytic approach will be used to combine the data. Specifically, drug- and country-specific estimates for the primary outcome measures will be assessed. In case of high heterogeneity between country-specific estimates for (a) certain active substance(s), an appropriate random-effect method will be used to derive a pooled estimate. In addition, the sensitivity of the overall pooled estimates to the inclusion or exclusion of certain country-specific estimates will be assessed. In some instances, it may not be appropriate to pool the data, and in such cases country-specific estimates will be excluded from the pooled estimate and presented separately.

9.7.3.5 Trends in the prescribing and monitoring practice of oral retinoids with respect to measures of the PPP

To identify ongoing trends in the countries of interest, ITS analysis using segmented regression will be performed in case the conditions for this analysis will be met (such as the number of time points in the pre-and post-implementation periods [at least 6 timepoints per period] and the number of observations per timepoint [at least 100] is available). Using ITS analysis, data will be evaluated at multiple time points before and after an intervention in order to detect whether or not an intervention had a significantly greater effect than any underlying trend.

The ITS analysis can assess the following key parameters:

- Proportion of episodes with contraception use for the month before treatment start
- Proportion of episodes with continuous concomitant use of contraception during the entire treatment episode
- Proportion of episodes with laboratory pregnancy tests at treatment start (up to 7 days before start date of oral retinoid prescription)
- Proportion of episodes with monthly laboratory pregnancy tests during treatment

A final decision on key parameters and time points for ITS analysis will be made based on results of analyses for primary outcomes. ITS analysis will be conducted for the outcomes only if sufficient data will be available for reliable results.

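### The complete-follow-up rule meets a fixed data end in December 2020 with no last start date, so whole-course outcomes can rise late in the post-implementation series without any change in practice

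*Protocol*

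**What the plan says.** Four parts of the protocol bear on this.

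- **Who is analysed (9.7.2).** The section opens with a broad aim: "It is aimed to include all patients with oral retinoid prescriptions in the analyses". It then sets a follow-up condition: "Analyses after treatment initiation will be performed for the following scenarios: (a) patients with a follow-up available covering the treatment episode". A second scenario asks for two further months of observation once the course is over.
- **When observation stops (9.7.1 and 9.1).** Follow-up runs to "transfer out of the database incl. death or the end of the study period, whichever comes first". For the post-implementation period, section 9.1 states: "This period captures the time starting after the distribution of EM until December 2020". The comparator is the two-year pre-referral period, July 2014 to June 2016: "This period will be used for the before and after comparison with the post-implementation period". Data continue after June 2016, but not after December 2020.
- **Which outcomes depend on the whole course (9.7.3.5).** The interrupted time series lists "Proportion of episodes with continuous concomitant use of contraception during the entire treatment episode" and, separately, monthly laboratory tests during treatment. It divides by all episodes in the interval, with no completeness condition. It does not say whether an episode belongs to the interval in which it starts, is active or stops. It asks for at least 6 points per period and 100 observations per point, and judges effectiveness at the 0.05 level.
- **What guards the data end.** Nothing does. The only sensitivity analysis on the post-implementation window (9.7.4) drops its first six months. The only shortage of follow-up acknowledged in 9.9.2 is the three years after acitretin.

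**The concern.** A course that starts in autumn 2020 can be seen in full only if it is very short. Two listed time-series outcomes are all-or-nothing over the course, and short courses pass such tests more easily. A completeness condition therefore enriches the last starting cohorts with easy passes.

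Dropping the condition does not help. If running courses are kept and scored on the time observed, the late courses are cut short and again pass more easily.

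At stake is the slope-change term of the segmented regression. An upward bend confined to the end of the post-implementation period is what a gradually effective programme would produce, and the protocol offers no analysis that would tell the two apart.

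**Working it through.** **The plan's own figures.** The protocol gives no course length, completion share or monthly adherence, so there is no plan figure for this point to reproduce. Its sample-size figure does reproduce (1.96² × 0.5 × 0.5 / 0.05² = 384.2, rounded up to 385), but it concerns precision only.

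**Assumptions, all outside the protocol.** No programme effect. Starts are uniform over time. Course length is log-normal with log-SD 0.5 and median 4, 6 or 8 months, limited to 1–24 months. Each treatment month is passed with probability 0.9, so a course of d months passes with probability 0.9^d: 0.81 for 2 months, 0.66 for 4, 0.53 for 6 and 0.43 for 8.

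**Step 1. Placement by start date, median 6 months (true value 49% throughout).**

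| Start quarter | Share complete | Mean length kept (months) | Pass, completed only | Pass, truncated kept |
|---|---|---|---|---|
| Q1 2019 | 99.5% | 7.2 | 49.5% | 49% |
| Q1 2020 | 84% | 6.1 | 54% | 50–51% |
| Q2 2020 | 61% | 5.2 | 59% | 53% |
| Q3 2020 | 22% | 3.8 | 67% | 62% |
| Q4 2020 | 0.4% | 2.0 | 79% | 81% |

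Both ways of handling late courses give the rise.

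**Step 2. Other placements (median 6).** By calendar activity, completed courses go from 44% to 49%. By stop date they stay at 49%. Start-date placement is therefore needed for the large effect.

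**Step 3. Segmented Poisson model with offset, 18 pre and 8 post quarters.** For completed courses the false slope ratio per quarter is 1.019 (median 4), 1.039 (median 6) and 1.061 (median 8). At median 6 it is 1.072 with a monthly pass of 0.8, 1.013 with 0.97, and 1.008 with little spread in length (log-SD 0.2).

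**Step 4. Apply the 100-per-point minimum.** At 300 starts per quarter and median 6, the last two quarters keep about 65 and 1 completed courses. Both fail the rule and six post points remain. The expected z falls from about 2.0 to about 1.3. Over medians 4 to 8 it is about 1.0 to 2.1.

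The figure of 300 is close to Germany in Table 5: 3,729 patients / 12 quarters = 311, if patients are read as starts. Sweden on the same reading gives 20,580 / 12 = 1,715 per quarter (patients there are non-unique). At that size z with the rule applied is about 2.9 (median 4), 4.7 (median 6) and 6.2 (median 8).

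Truncated courses never fall below 100 for this reason and give larger values: about 5 at 300 starts and median 6, and 6.9 to 18.1 at 1,715.

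**Step 5. Before-after percentage for an all-or-nothing outcome.** If pre-referral courses are followed past June 2016 while post courses must be complete by December 2020, the bias is +1.7, +3.1 and +4.7 points for medians 4, 6 and 8. If pre-referral courses are cut at June 2016 in the same way, it is 0.

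**Step 6. An outcome that moves the other way.** For any test during treatment, with an assumed 15% chance per month, the completed-course figure falls from 65% to 61%, 56%, 46% and 31% over the four quarters of 2020.

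**The case against.** The case against is substantial and parts of it stand.

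- **The protocol does not fix the setting that produces the effect.** A reader might infer that the time series will certainly be scored on completed courses placed by start date. Section 9.7.3.5 divides by all episodes and is silent on placement. This stands. What remains is that 9.7.2 and 9.7.3.5 conflict, and with start-date placement both give the artefact.
- **The 100-per-point rule removes the worst points.** It does so for completed courses in a database the size of the German one, where z is then mostly below 1.96. It does not in a database the size of the Swedish one, nor for truncated courses anywhere.
- **The primary percentages are not all inflated.** A reader might infer an upward bias across section 9.7.2. That is unsupported. The any-test measure would fall. The contraceptive measure there is concomitant use, without the whole-episode wording of 9.7.3.5. The before-after bias also needs one reading of the phrase "the end of the study period, whichever comes first", which may mean each period or the whole study.
- **The acitretin limitation is not an admission of the problem.** Section 9.9.2 speaks only of the three years after acitretin and says nothing of courses still running at June 2016.
- **The time series is secondary and conditional, and detail may sit in the SAP.** This is fair for episode placement and trimming of time points. The follow-up condition itself, however, is a rule stated in the protocol. Section 9.7.2 also already plans test frequency by month of treatment, which is close to the remedy for tests.

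**Conclusion.** The concern holds in a limited form. Section 9.7.2 imposes complete follow-up, data stop in December 2020, nothing sets a last start date, and 9.7.3.5 uses a denominator without that condition. With start-date placement, continuous contraception and monthly testing rise at the end of the series with no change in practice, by a slope ratio of about 1.02 to 1.06 per quarter for completed courses (medians 4 to 8 months, log-SD 0.5, monthly pass 0.9).

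Whether that crosses 0.05 depends on database size. It is uncertain at 300 starts per quarter and likely at about 1,700. The before-after figure for monthly testing is inflated by about 2 to 5 points only if the two periods are cut differently.

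The documents do not support a claim that a false finding of effectiveness is assured, or that every outcome is biased upward. All sizes rest on assumed course lengths and adherence. This should be fixed before extraction, but it is not a fatal flaw.

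**What to change.** 1. State in 9.7.3.5 whether episodes are placed by start, activity or stop, and make its denominator agree with 9.7.2.
2. Score during-treatment outcomes per treatment month, using every observed month up to stop or censoring, with no completed-course condition.
3. For whole-course and after-stop outcomes, require the same minimum potential follow-up from start in both periods, for example starts at least 6 to 12 months before each period's data end, and end the time series for those outcomes at that date.
4. State in 9.7.1 which period end censors follow-up.

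The length of the cut matters. With 12 months, pass rates among completed and all courses are 60.7% against 60.6% (median 4), 50.0% against 49.1% (median 6) and 42.7% against 40.5% (median 8). Six months is only a partial cure if courses typically last that long: at median 6 it leaves the six-quarter fit of Step 4, with a slope ratio still near 1.03. The cut could be set from pre-period course durations before post-period outcomes are seen.

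**Cost.** Wording, and the loss of a few late points for whole-course outcomes. A 12-month cut leaves four quarterly post points, so two-monthly points (six) or monthly points (twelve) are needed to keep at least 6. On Table 5 counts read as starts over 36 months, two-monthly points hold about 3,729 / 18 = 207 (Germany), 4,842 / 18 = 269 (Spain) and 20,580 / 18 = 1,143 (Sweden) for all substances together, above the minimum of 100. A cut of 6 months keeps six quarterly points. The per-month outcomes lose nothing.
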